3.1 Background information

3.1.1 Haemophilia

Haemophilia is an inherited bleeding disorder characterised by an increased bleeding tendency, typically in weight bearing joints. Haemophilia A is caused by a partial or complete deficiency of blood coagulation factor VIII (FVIII) and haemophilia B is caused by defect factor IX (FIX). Inheritance is chromosome X-linked and recessive; therefore the disease mainly affects males. The incidence of haemophilia A and B on average is estimated to be about 1 in 5000 live male births⁴. According to the World Federation of Haemophilia global survey of 2014, about 178,500 persons are diagnosed with haemophilia worldwide. Of these, about 80% have haemophilia A.

Haemophilia is classified as “severe”, “moderate” or “mild” according to the plasma activity level of the affected coagulation factor⁵. With a deficiency of FVIII or FIX, the degree of activation of coagulation factor X (FX) becomes insufficient. Consequently, the thrombin burst is delayed and insufficient for normal haemostasis⁶. The haemostatic plug, if formed, in these patients is fragile and easily dissolved by normal fibrinolytic activity. This leads to impaired haemostasis and spontaneous prolonged bleeding episodes. In severe haemophilia, bleeding in joints occurs spontaneously and is the most frequent symptom of the disease. Recurrent bleeding episodes in the same location - most commonly a weight bearing joint - lead to chronic arthropathy, muscular atrophy and deformities. Treatment of bleeding episodes as they manifest (on-demand treatment) may delay arthropathy, but does not prevent it. The majority of children with severe haemophilia experience their first bleeding episode in a joint prior to the age of 4 years. Many children also bleed from other body sites, also before this age is reached⁷. For this reason, primary prophylaxis treatment with regular FVIII injections in the non-bleeding state is the recommended from early childhood.

The most common complication of replacement therapy is development of antibodies binding to FVIII. These binding antibodies might neutralise the exogenous of FVIII and are then called inhibitors. In patients who have developed inhibitors towards FVIII, replacement therapy is

Protocol
 Trial ID: NN7415-4255
 UTN: U1111-1179-3872
 EudraCT no.: 2016-000614-29

~~CONFIDENTIAL~~

Date: 28 December 2017
 Version: 4.0
 Status: Final
 Page: 22 of 124

Novo Nordisk

rendered ineffective. These patients may be treated with bypassing agents, recombinant FVII (NovoSeven[®]) and activated prothrombin complex concentrate (FEIBA[®]) given as intravenous (i.v.) injections.

Current treatment options in haemophilia A, includes replacement therapy or by-passing therapy are hampered by the fact that these products must be given as i.v. injections. Bypassing agents are characterized by relatively short half-lives, therefore prophylactic treatment is burdensome. A new therapeutic agent that can be administered subcutaneously will represent a major improvement in the treatment of these patients in a prophylaxis setting.

3.1.2 Concizumab

The trial product, concizumab, is a humanised recombinant monoclonal antibody (mAb) of the immunoglobulin G4 (IgG4) isotype with a molecular weight of 149 kilo Daltons. Like other antibodies, concizumab is composed of two light chains and two heavy chains linked together by disulfide bridges. To prevent formation of half-antibodies, the serine at position 241 in the heavy chain has been replaced with a proline (S241P (Kabat annotation)). The mechanism of action of concizumab is based on the concept of inhibiting the activity of a natural coagulation inhibitor, tissue factor pathway inhibitor (TFPI). TFPI is a potent inhibitor of the initiation phase of the coagulation process, i.e. the activation of FX to FXa by the tissue factor (TF)/factor VIIa (FVIIa) complex. TFPI first binds to and inhibits activated FXa and subsequently binds to and inhibits the TF/FVIIa complex, forming a TF/FVIIa/FXa/TFPI complex. Thus, concizumab prevents both inhibition of FXa and inhibition of FVIIa/TF by TFPI. In this manner, sufficient amounts of FXa to ensure effective haemostasis in the absence of a functional activated factor IX/activated factor VIII (FIXa/ FVIIIa) complex may be generated. This is a new concept that remains to be documented safe and efficacious in patients with haemophilia. More information about the physiological role of TFPI and the mode of action of concizumab is provided in the Investigator's Brochure (IB).

Key differentiator is thus a new mode of action (MoA), and the key benefit of concizumab in patients with severe haemophilia A is reduced treatment burden due to subcutaneous (s.c.) administration potentially leading to better adherence, more patients on prophylactic treatment and ultimately better outcome.

Four clinical trials with concizumab have been completed thus far: the first-human-dose trial (NN7415-3813, explorer^{TM1}), a single dose trial in Japanese healthy subjects (NN7415-3981), a multiple dose trial NN7415-3986 (explorer^{TM2}), and NN7415-4159 (explorer^{TM3}). When the first cohort with four healthy subjects in explorer^{TM2} was completed, prior to the initiation of the 2nd cohort, the trial was halted due to findings related to thrombosis in an ongoing 26-week toxicity study in primates. In this study animal had plasma concentrations several hundred folds above clinically relevant concentrations. Follow up investigations confirmed that the animal's condition was related to thrombosis in the lungs caused by exaggerated pharmacology at these high plasma concentrations. Before the initiation of the fourth phase 1 trial (, explorer^{TM3}) a new 52-week non-

Protocol
Trial ID: NN7415-4255
UTN: U1111-1179-3872
EudraCT no.: 2016-000614-29

~~CONFIDENTIAL~~

Date:	28 December 2017	Novo Nordisk
Version:	4.0	
Status:	Final	
Page:	23 of 124	

clinical toxicology study was conducted in primates to investigate the findings in the previous study. The conclusion from this new non-clinical study was that the results from non-clinical studies support further clinical development of concizumab. Explorer^{TM3} was a multiple-dose clinical trial, which aimed to investigate the safety, pharmacokinetics and pharmacodynamics of concizumab at five different dose levels in adult severe haemophilia A patients without inhibitors. In this trial multiple doses of concizumab were administered s.c. over a period of six weeks. Doses of up to 0.8 mg/kg administered every four days did not raise safety concerns and a decision not to dose-escalate to a 1.1 mg/kg dose-cohort was taken. For further information, please refer to the Investigator's Brochure.

The explorer^{TM3} trial was finalised following the completion of cohort 3 (0.8 mg/kg sc every 4 days for 6 weeks). Blinded preliminary safety and PK/PD data from the cohort was reviewed by the concizumab safety committee. Marked changes in coagulation parameters were observed including a decrease from baseline in fibrinogen and a pronounced increase in D-dimer and F1+2 outside of normal range. In addition, a substantial inter subject variation in pro-coagulant response to the drug was observed. Based on this, the Novo Nordisk safety committee (see section [12.8.1](#)) decided not to proceed to cohort 4 (1.1 mg/kg sc every 4 days for 6 weeks). No clinical consequences or serious adverse were seen in the completed cohorts in explorer3.

The PK results from explorer^{TM3} showed exposure-response in terms of fewer bleeding episodes recorded for patients who reached plasma concentrations of concizumab above 100 ng/mL. Individual predicted PK profiles merged with recorded spontaneous and traumatic bleeding episodes are shown in [Figure 3-1](#).

Protocol
 Trial ID: NN7415-4255
 UTN: U1111-1179-3872
 EudraCT no.: 2016-000614-29

~~CONFIDENTIAL~~

Date: 28 December 2017
 Version: 4.0
 Status: Final
 Page: 24 of 124

Novo Nordisk

Figure 3–1 Individual predicted PK profiles based on data merged with recorded spontaneous (circles) and traumatic (triangles) bleeding episodes during the dosing period and follow-up period.

All data originates from explorerTM3 (N=24 patients). PK of concizumab is subdivided into three exposure levels of ≤ 20 ng/mL, 20-100 ng/mL, and > 100 ng/mL together with the number of contributing patients. LLOQ: lower limit of quantification. ^a ‘Time in trial’ refers to the time that the patients spent on each concizumab exposure level, and the ≤ 20 ng/mL level therefore also includes the screening period (not shown on this figure).

A large difference between the peak and trough plasma concentrations of concizumab were observed as well, especially in the highest dose group (0.80 mg/kg) of explorerTM3. In patients who received 0.25, 0.5 and 0.8 mg/kg doses a significant overlap in plasma concentrations of concizumab was seen due to high between-patient variability in concizumab.

Single doses of concizumab up to 9 mg/kg have been administered to haemophilia patients in the first human dose trial with concizumab, explorerTM1. These doses resulted in plasma concentrations of concizumab that were significantly higher than the ones that are modelled to be reached in the highest escalated daily dose (0.25 mg/kg) of explorerTM5.

For an assessment of benefits and risks of the trial, see Section [18.1](#).

For further information, please refer to the Investigator’s Brochure.

3.2 Rationale for the trial

Four phase 1 clinical trials with concizumab have been finalised. Key safety and preliminary efficacy results from these phase 1 trials support further development of concizumab in haemophilia

Protocol
Trial ID:NN7415-4255
UTN:U1111-1179-3872
EudraCT no.:2016-000614-29

~~CONFIDENTIAL~~

Date:	28 December 2017	Novo Nordisk
Version:	4.0	
Status:	Final	
Page:	25 of 124	

patients. Therefore, the main objective in the phase 2 of concizumab development is to assess efficacy and safety and provide data that will guide for the confirmatory phase 3 concizumab trials.

Protocol
Trial ID:NN7415-4255
UTN:U1111-1179-3872
EudraCT no.:2016-000614-29

~~CONFIDENTIAL~~

Date: 28 December 2017
Version: 4.0
Status: Final
Page: 26 of 124

Novo Nordisk

4 Objective(s) and endpoint(s)

4.1 Objective(s)

4.1.1 Primary objective

- To assess the efficacy of concizumab administered s.c. once daily in preventing bleeding episodes in patients with severe haemophilia A without inhibitors

4.1.2 Secondary objectives

- To assess the long-term efficacy of concizumab in patients with severe haemophilia A without inhibitors
- To assess the safety of concizumab in patients with severe haemophilia A without inhibitors
- To assess the immunogenicity of concizumab in patients with severe haemophilia A without inhibitors

4.2 Endpoint(s)

4.2.1 Primary endpoint

- The number of bleeding episodes during at least 24 weeks from treatment onset
-

4.2.2 Secondary endpoints

4.2.2.1 Supportive secondary endpoints

- **Supportive secondary efficacy endpoints**
- The number of bleeding episodes during 76 weeks from treatment onset
- The number of spontaneous bleeding episodes during at least 24 weeks from treatment onset
- The number of spontaneous bleeding episodes during 76 weeks from treatment onset
- **Supportive secondary safety endpoints**
- Number of treatment-emergent adverse events (TEAEs) during at least 24 weeks from treatment onset
- Number of TEAEs during 76 weeks from treatment onset
- Occurrence of anti-concizumab antibodies during at least 24 weeks from treatment onset
- Occurrence of anti-concizumab antibodies during 76 weeks from treatment onset
-
- Change from baseline of fibrinogen during 24 weeks from treatment onset
- Change from baseline of fibrinogen during 76 weeks from treatment onset
- Change from baseline of D-dimer during 24 weeks from treatment onset
- Change from baseline of D-dimer during 76 weeks from treatment onset

Protocol
 Trial ID: NN7415-4255
 UTN: U1111-1179-3872
 EudraCT no.: 2016-000614-29

~~CONFIDENTIAL~~

Date: 28 December 2017
 Version: 4.0
 Status: Final
 Page: 27 of 124

Novo Nordisk

- Change from baseline of prothrombin fragment 1 + 2 (F1 + 2) during 24 weeks from treatment onset
- Change from baseline of F1 + 2 during 76 weeks from treatment onset
- Change from baseline of prothrombin time (PT) during 24 weeks from treatment onset
- Change from baseline of PT during 76 weeks from treatment onset
- Change from baseline of activated partial thromboplastin time (APTT) during 24 weeks from treatment onset
- Change from baseline of APTT during 76 weeks from treatment onset
- Change from baseline of antithrombin (AT) during 24 weeks from treatment onset
- Change from baseline of AT 76 weeks from treatment onset
-

Supportive secondary pharmacokinetic endpoints

- Concentration of concizumab prior to the last dose administration at 24 weeks
- Concentration of concizumab prior to the last dose administration at 76 weeks

Supportive secondary pharmacodynamic endpoints

Plasma free TFPI concentration

- Value prior to the last dose administration at 24 weeks
- Value prior to the last dose administration at 76 weeks

Thrombin generation

- Peak thrombin generation (nM) prior to the last dose administration at 24 weeks
- Peak thrombin generation (nM) prior to the last dose administration at 76 weeks
- Endogenous thrombin potential (nM*min) prior to the last dose administration at 24 weeks
- Endogenous thrombin potential (nM*min) prior to the last dose administration at 76 weeks
- Velocity index (nM/min) prior to the last dose administration at 24 weeks
- Velocity index (nM/min) prior to the last dose administration at 76 weeks

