17.6 Secondary endpoints

17.6.1 Supportive secondary efficacy endpoints

- The number of bleeding episodes during 76 weeks from treatment onset.
- The number of spontaneous bleeding episodes during at least 24 weeks from treatment onset.
- The number of spontaneous bleeding episodes during 76 weeks from treatment onset.

The supportive secondary endpoints will be estimated using the same negative binomial regression model as the primary endpoint.

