4.2.3.3 Exploratory pharmacokinetic and pharmacodynamic endpoints

- Concentration of concizumab over time during 24 hours PK assessment
- Concentration of free TFPI over time during 24 hours PD assessment
- Thrombin generation over time during 24 hours PD assessment
 - Peak of thrombin generation time during 24 hours PD assessment
 - ETP time during 24 hours PD assessment
 - Velocity index time during 24 hours PD assessment

All endpoints referring to a time frame of either 24 weeks or of at least 24 weeks will be evaluated in the main part of the trial.

All endpoints referring to a time frame of 76 weeks will be evaluated in the extension part of the trial.

Protocol
 Trial ID: NN7415-4255
 UTN: U1111-1179-3872
 EudraCT no.: 2016-000614-29

~~CONFIDENTIAL~~

Date:
 Version:
 Status:
 Page:

28 December 2017
 4.0
 Final
 29 of 124

Novo Nordisk

5 Trial design

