5.1 Type of trial

The trial is a multicentre single-arm trial, which aim to evaluate the efficacy and safety of concizumab 0.15 mg/kg (with potential dose escalation to 0.20 and 0.25 mg/kg) administered daily s.c. in patients with severe haemophilia A without inhibitors. The selected dose regimen is based on relevant PK and TFPI data as well as PK/PD modelling from the preceding explorer™ trials. Both on-demand and prophylaxis patients will be eligible for the trial.

[figure not shown]

Figure 5–1 Schematic diagram of the trial design

The total trial duration for the individual patient will be approximately 86 weeks, including a 2-week screening period, a subsequent 76-week treatment period and an 8-week follow-up period, see [Figure 5–1](#).

The 76 weeks treatment period is further split into a main part which lasts at least 24 weeks for all patients in the trial and an extension part which lasts 52 weeks. After completion of the main part of the trial, patients will continue into the extension part. All available data up to the time point where the last patients ends 24 weeks of treatment (or have withdrawn) will be used in the analysis of the main part, see Section [17.7](#).

Breakthrough bleeding episodes occurring from visit 1 to end-of-trial visit will be treated by the patients at home with FVIII at the discretion of the investigator, who will also choose dose levels. Only turoctocog alfa/NovoEight® will be provided and paid by Novo Nordisk for this purpose.

The analysis of the main part (after 24 weeks) of the trial aims to substantiate CPoC that concizumab has the potential to prevent bleeding episodes in patients with severe haemophilia A without inhibitors. The extension part will provide additional safety data on 52 weeks dosing of concizumab.

Protocol
 Trial ID:NN7415-4255
 UTN:U1111-1179-3872
 EudraCT no.:2016-000614-29

~~CONFIDENTIAL~~

Date: 28 December 2017
 Version: 4.0
 Status: Final
 Page: 30 of 124

Novo Nordisk

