5.2 Rationale for trial design

ExplorerTM5 is a phase 2, clinical proof of concept (CPoC) and safety trial. The trial aims to substantiate CPoC that concizumab has the potential to prevent bleeding episodes in haemophilia patients without inhibitors. A dose escalation design will allow cautious dose escalation in order to choose the efficacious and safe concizumab dose for the individual patient from the selected dose regimen Concizumab 0.15 mg/kg (with two potential dose-escalation steps, 0.20 mg/kg and 0.25 mg/kg) given s.c. once daily will be investigated.

The duration of 24 weeks for the main part of the trial is deemed necessary in order to obtain information on the annual bleeding rate (ABR) during concizumab prophylaxis. The duration of the extension part of the trial will be 52 weeks and will provide further information on long-term efficacy, i.e. ABR, and also provide additional safety data upon 76 weeks treatment with concizumab.

A total of 33 patients are planned to receive concizumab s.c. once daily in this single arm trial, please see [Figure 5-1](#).

The concizumab dose regimens will be starting with 0.15 mg/kg with the possibility to escalate to 0.20 mg/kg and 0.25 mg/kg, see section [5.3.1](#).

Protocol
 Trial ID: NN7415-4255
 UTN: U1111-1179-3872
 EudraCT no.: 2016-000614-29

~~CONFIDENTIAL~~

Date:	28 December 2017	Novo Nordisk
Version:	4.0	
Status:	Final	
Page:	31 of 124	

Daily dosing with 0.15 mg/kg aims to ensure steady-state levels of concizumab plasma concentrations above 100 ng/mL for the majority of the patients starting on this dose. The PK results from explorerTM3 showed exposure-response in terms of fewer bleeding episodes recorded for patients who reached plasma concentrations of concizumab above 100 ng/mL see [Figure 3-1](#). The minority of patients which are predicted to have steady-state plasma concentrations below this threshold are expected to experience bleeding episodes and therefore will have the opportunity to be dose-escalated to the dose of 0.2 mg/kg. A further dose escalation to 0.25 mg/kg per day is permitted, again based on the bleeding rate, see section [5.3.1](#).

Figure 5-2 Individual predicted concizumab concentration profiles for all concizumab-treated patients in explorerTM2 (n=4 patients) and explorerTM3 (n=18 patients). The horizontal lines indicate 100 ng/mL, and the shaded areas represent the full range (min-max) of the individual predicted profiles¹.

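### Both long-term bleeding endpoints count from first dose to week 76, so a change in bleed rate during the extension is diluted by roughly a third to a half, and no extension-period rate is stated

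*Protocol*

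**What the plan says.** Protocol section 4.1.2 lists as a secondary objective: "To assess the long-term efficacy of concizumab in patients with severe haemophilia A without inhibitors". Section 5.2 says that the extension "will provide further information on long-term efficacy, i.e. ABR".

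The primary endpoint (section 4.2.1) is "The number of bleeding episodes during at least 24 weeks from treatment onset". Only two bleeding endpoints reach beyond the main part, both in section 4.2.2.1: "The number of bleeding episodes during 76 weeks from treatment onset" and "The number of spontaneous bleeding episodes during 76 weeks from treatment onset". On analysis, section 17.6.1 says: "The supportive secondary endpoints will be estimated using the same negative binomial regression model as the primary endpoint". That model (section 17.3) fits a single rate, with main-part exposure as the offset.

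Section 5.1 describes a "main part which lasts at least 24 weeks for all patients in the trial and an extension part which lasts 52 weeks". Section 4.2.3.3 adds: "All endpoints referring to a time frame of 76 weeks will be evaluated in the extension part of the trial". This fixes when the endpoints are evaluated. It does not move their start, which is treatment onset.

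Section 17 is visible only in version 3 (18 December 2017). The endpoint list is the same in version 4.0.

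**The concern.** A long-term efficacy objective asks whether the effect lasts. An estimate that starts at first dose answers a different question: the average rate over the whole treatment period. It re-counts all the time already used for the primary endpoint, including the 2-week run-in and the time before any dose escalation. The protocol itself leaves that time out of its first proof-of-concept criterion.

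The average can mislead in both directions. If the effect wanes, the main part pulls the figure down. If titration works, early bleeds pull it up and the maintenance rate looks worse than it is. The protocol states no bleed rate for the extension, no confidence interval for one and no contrast between periods. The dose-level and PK/PD analyses in section 17.5 are additions to the primary endpoint only.

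**Working it through.** **The plan's own figure.** The protocol gives none for the 76-week endpoints. The nearest is the 95% power for the first proof-of-concept criterion (section 17.1: ABR 4, over-dispersion 6, 30 patients, 6 months, threshold 12). Reading over-dispersion as variance divided by mean, the mean count per patient is 4 × 0.5 = 2 and SE(log rate) = √(6/(30 × 2)) = 0.316. Power = Φ(ln(12/4)/0.316 − 1.96) = Φ(1.51) = 93.5%. Simulating the fitted negative binomial model gives 95.5%. So the model is being read as the protocol intends.

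**Share of exposure already used.** Let w be main-part weeks divided by 76.
- Minimum main part: w = 24/76 = 31.6%.
- Expected average of 8 months (section 17.1, second criterion): 8 × 365.25/12/7 = 34.8 weeks, so w = 45.8%.

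**Dilution.** For a patient treated for all 76 weeks, cumulative ABR = w × main-part ABR + (1 − w) × extension ABR. The main-part value of 4 is the protocol's assumption for the end dose. The extension values are my assumptions.

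| Extension ABR | Reads as, 24-week main part | Reads as, 8-month main part |
|---|---|---|
| 8 | (24×4 + 52×8)/76 = 6.7 | 0.458×4 + 0.542×8 = 6.2 |
| 10 | 8.1 | 7.3 |
| 12 | (24×4 + 52×12)/76 = 9.5 | 0.458×4 + 0.542×12 = 8.3 |

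The protocol's assumption for all main-part time, including time before escalation, is 5.4 rather than 4. With 5.4 over 8 months, extension rates of 8 and 12 read as 6.8 and 9.0. The share absorbed is unchanged. In the other direction, 5.4 in the main part followed by 4 in the extension reads as 0.458×5.4 + 0.542×4 = 4.6, above the true maintenance rate.

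**Is a separate estimate feasible?** With 30 patients at ABR 4, all completing, about 30×4×24/52 = 55 bleeds are expected in weeks 0–24 and 30×4×52/52 = 120 in weeks 24–76. If each patient's underlying rate is shared across periods, SE(log rate ratio) = √(1/55.4 + 1/120) = 0.16, so the 95% limits are the estimate times or divided by about 1.37. This is a best case, because patient-by-period variation and dropout widen it. In simulations with 30 patients, a plain patient-clustered standard error rejected a true null about 6–12% of the time instead of 5%. A small-sample correction or a random-effect model is therefore needed, and I give no power figure.

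**The case against.** The strongest reply is that little is lost. The main-part ABR is estimated separately with its own confidence interval (section 17.3), and the final report is to describe both parts (section 17.8). On the numbers above, a reader would see 4 and then 6.7 or 9.5 (8-month main part: 6.2 or 8.3), which is plainly a rise, and could subtract the counts. Other signals of lost effect exist: antibodies over both time frames; concizumab trough, free TFPI and thrombin generation at weeks 24 and 76; and records of escalation and of reasons for discontinuation. A statistical analysis plan, not shown, could add a period summary. All of this stands, and it limits the point. It does not supply an interval or a within-patient contrast for the extension, and the endpoint window itself is fixed in the protocol.

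A second objection concerns the remedy. A rate among patients still on treatment after week 24 drops early failures, whom the cumulative rate keeps. A comparison of weeks 0–24 with 24–76 also sets titration against maintenance, so successful titration can mask waning. Both are right. They are reasons to supplement the 76-week endpoints, not to replace them.

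A reader might go further and infer that loss of efficacy is averaged away, or that a drug drifting to the failure threshold would be passed as effective. It is true that the cumulative point estimate reaches 12 only when the extension ABR reaches 15.7 (24-week main part) or 18.8 (8 months). But the threshold of 12 belongs to the two proof-of-concept criteria assessed at the end of the main part. Section 17.8 rests the proof-of-concept and phase 3 dose conclusions there, and no threshold or decision attaches to the 76-week endpoints. The documents do not support the stronger reading.

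**Conclusion.** The point holds as one of dilution. The two long-term bleeding endpoints carry 32% to about 46% of their exposure from the primary-endpoint period, so a change in the extension shows at only 54–68% of its size. The shares assume that patients complete 76 weeks and that the main part averages between 24 weeks and 8 months. The ABR readings also rest on the main-part rate of 4 and the illustrative extension rates.

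Excluding data after discontinuation of trial product (section 17.3) adds some masking, since patients who lose efficacy on the top dose must stop. A late-period rate would share that limit. There is also a wording fault: the primary model's main-part offset cannot apply unchanged to a 76-week count. The endpoints are supportive and the proof-of-concept conclusion is untouched, so this is a worthwhile improvement and not a threat to the trial's main result.

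**What to change.** - Keep the two 76-week endpoints, and state total exposure over the counted period as their offset.
- Add, for all treated bleeds and for spontaneous bleeds, the ABR with 95% confidence interval after each patient's own week 24.
- Add a within-patient rate ratio of later to earlier time, from a model with a patient random effect or a robust standard error corrected for small samples.
- Leave the 2-week run-in and pre-escalation time out of the earlier period, or show the ratio with and without it, so that titration is not read as sustained effect. Escalation can also occur after week 24, so list the number of escalations in each period.
- State the downside: the late-period rate applies only to patients still on treatment after week 24. Report it beside the number of and reasons for earlier discontinuations, and beside the cumulative rate.

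The cost is a few sentences and one extra model per endpoint on data already collected, with no new visits or patients.
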